### 4. Nutritional status

Determine if the patient has experienced weight loss during the last 6 months and calculate the patient's body mass index (BMI). If one of the test is abnormal, the nutritional status is considered impaired.

Unintentional weight loss in the last six months?

☐ YES ☐ NO

BMI = weight (kg) / height (m)

### 5. Cognitive status - Mini-Cog™

#### Instructions for administration and scoring

##### Step 1: Three word registration

Look directly at the person and say, "Please listen carefully. I am going to say 3 words that I want you to repeat back to me now and try to remember. The words are [select a list of words from the versions below]. Please say them for me now". If the person is unable to repeat the words after three attempts, move to Step 2 (clock drawing).

The following and other word lists have been used in one or more clinical studies. For repeated administrations, use of an alternative word list is recommended.

Version 1	Version 2	Version 3	Version 4	Version 5	Version 6
Banana	Leader	Village	River	Captain	Daughter
Sunrise	Season	Kitchen	Nation	Garden	Heaven
Chair	Table	Baby	Finger	Picture	Mountain

### Step 2: Clock drawing

Say, "Next I want you to draw a clock for me. First, put in all of the numbers where they go". When that is completed, say, "Now, set the hands to 10 past 11".

Use the pre-printed circle provided for this exercise. Repeat instructions as needed as this is not a memory test. Move to step 3 if the clock is not complete within three minutes.

### Step 3: Three word recall

Ask the person to recall the three words you stated in Step 1. Say "What were the three words I asked you to remember?" Record the word list version number and the person's answers below.

Word list version: \_\_\_\_\_ Patients answers \_\_\_\_\_

### Scoring

Word recall: _____ (0-3 points)	1 point for each word spontaneously recalled without cueing
Clock draw: _____ (0 or 2 points)	Normal clock = 2 points. A normal clock has all numbers placed in the correct sequence and approximately correct position (e.g. 12, 3, 6, 9 are in anchor positions) with no missing or duplicate numbers. Hands are pointing to the 11 and 2 (11:10). Hand length is not scored.  Inability or refusal to draw a clock (abnormal) = 0 points
Total score: _____ (0-5 points)	Total score = Word recall score + Clock draw score.  A cut point of <3 in the Mini-Cog has been validated for dementia screening, but many individuals with clinically meaningful cognitive impairment will score higher. When greater sensitivity is desired, a cut point of <4 is recommended as it may indicate a need for further evaluation of cognitive status.

Mini-Cog™ © S. Borson. All rights reserved. Reprinted with permission of the author solely for clinical and educational purposes. May not be modified or used for commercial, marketing, or research purposes without permission of the author ([contact]). v. 01.19.16

## 6. Depressive mood: Mini-Geriatric Depression Scale

The patient's depressive mood will be assessed using the Mini-GDS ([Cheng, 2005](#); [Clément, 1997](#)).

Mini-GDS			Score
1. Are you basically satisfied with your life?	YES = 0	NO = 1	
2. Do you feel that your life is empty?	YES = 1	NO = 0	
3. Do you feel happy most of the time?	YES = 0	NO = 1	
4. Are you afraid that something bad is going to happen to you?	YES = 1	NO = 0	
		Total	 / 4

### Interpretation

0 = not depressed.

1 = uncertain.

2 to 4 = depressed

## 7. Comorbidities: Updated Charlson Comorbidity Index

Comorbidities will be assessed using the Charlson comorbidity index updated according to Quan *et al.* ([Quan, 2011](#)).

Check the item when the patient presents the comorbid condition, and add each point to obtain the total score. Cancer or hematological malignancy should also be scored.

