### Geriatric status

Patient geriatric status will be evaluated using the G8 screening tool, G-CODE assessment tool and CISR-G comorbidity assessment tool.

- The G8 screening tool ([Soubeyran, 2008](#); Appendix 7) was developed to separate fit older cancer patients who were able to receive standard treatment from those that should undergo a geriatric assessment to guide tailoring of therapy. It consists of a short, nurse-administered survey of eight questions to establish: appetite, weight loss, BMI, mobility, mood and cognition, number of medications, patient-related health, age categories.
- The G-CODE ([Paillaud, 2018](#); Appendix 8) is a core set of commonly used tools/items for geriatric assessment which has been validated for the collection of geriatric data in clinical cancer trials of older adults, enabling comparison across trials. The tools/items proposed in G-CODE are:

- (i) Social assessment: living alone or support requested to stay at home;

- (ii) Functional autonomy: Activities of Daily Living (ADL) questionnaire and short instrumental ADL questionnaire (4-IADL);
  - (iii) Mobility: Timed Up and Go test;
  - (iv) Nutrition: weight loss during the past 6 months and body mass index;
  - (v) Cognition: Mini-Cog test;
  - (vi) Mood: mini-Geriatric Depression Scale;
  - (vii) Comorbidity: updated Charlson Comorbidity Index.
- The CISR-G (Miller, 1992; Appendix 9) is a nurse administered questionnaire to record and score the medical and psychiatric impairment of older patients to quantify the overall burden of disease (comorbidity)

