#### **10.3.5. Geriatric status**

Patient autonomy will be evaluated using ADL and 4-IADL evaluations. Change over time in ability to perform ADL and IADL will be investigated.

For exploratory purposes, Time to definitive deterioration in ADL will be compared. Time to definitive deterioration of ADL will be defined as the interval between randomisation and the first decline in the ADL score  $\geq 2$  points compared to the ADL at inclusion with no further improvement in score  $\geq 2$  points. Progression or death will be considered as an event.

In a complementary analysis, competing risks approach will be used to decompose Time to definitive deterioration of ADL considering death and progression as a competing event.

Change over time in other geriatric parameters will be investigated.

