### Clinical condition

	Metastatic solid tumour	6 points
	AIDS / HIV	4 points
	Moderate / severe liver disease	4 points
	Any malignancy, including leukemia and lymphoma	2 points
	Mild liver disease	2 points
	Hemiplegia or paraplegia	2 points
	Congestive heart failure	2 points
	Dementia	2 points
	Chronic pulmonary disease	1 point
	Rheumatologic disease	1 point
	Renal disease	1 point
	Diabetes with chronic complications	1 point

Score   / 24

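### The Charlson form's add-everything instruction scores the study cancer 8 instead of 6 and does not fit its own 24-point scale (minor)

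*Protocol*

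**What the plan says.** Appendix 8 section 7 of the protocol gives the rule for the updated Charlson index: "Check the item when the patient presents the comorbid condition, and add each point to obtain the total score". It then adds: "Cancer or hematological malignancy should also be scored". The list beneath has twelve conditions with weights from 6 down to 1, and ends in a total out of 24.

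Two pairs of lines on that list are grades of one condition:

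- "Metastatic solid tumour" (6 points) and "Any malignancy, including leukemia and lymphoma" (2 points)
- "Moderate / severe liver disease" (4 points) and "Mild liver disease" (2 points)

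The protocol nowhere states that one line of a pair replaces the other.

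Section 6.3 lists the index among the G-CODE components ("Comorbidity: updated Charlson Comorbidity Index"). The schedule of visits has the G-CODE at screening, Day 120, Day 240, later treatment visits and end of treatment. Section 3.2.2 makes geriatric status by G-CODE an other secondary endpoint. Section 10.3.5 names ADL and 4-IADL and covers the rest with one sentence: "Change over time in other geriatric parameters will be investigated".

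**The concern.** De novo metastatic disease is inclusion criterion 4, so every eligible patient meets both cancer lines when they are read literally. The sentence requiring cancer to be scored does not say which line to use, and its wording is close to the 2-point line, so it invites a second tick. A rater who follows the instruction records 8 for the study cancer. A rater guided by the printed maximum of 24 records 6.

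At stake is the meaning of the reported comorbidity score. Two points is the form's full weight for dementia or congestive heart failure. If the reading differs between sites, patients with the same health get different scores. If it differs between visits of one patient, a change appears without any clinical event.

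The protocol did see a similar problem in the other comorbidity scale. For the CISR-G, where the manual generally rates prostate carcinoma at 4, the eligibility criteria state that genitourinary score 4 does not apply. The Charlson form has no such rule.

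**Working it through.** **Inputs** (all from Appendix 8 section 7)

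| Condition | Weight |
|---|---|
| Metastatic solid tumour | 6 |
| AIDS/HIV | 4 |
| Liver disease, moderate or severe | 4 |
| Any malignancy | 2 |
| Liver disease, mild | 2 |
| Hemiplegia or paraplegia | 2 |
| Congestive heart failure | 2 |
| Dementia | 2 |
| Chronic pulmonary disease | 1 |
| Rheumatologic disease | 1 |
| Renal disease | 1 |
| Diabetes with chronic complications | 1 |

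**Step 1. Reproduce the stated maximum of 24 under the printed instruction.**
6 + 4 + 4 + 2 + 2 + 2 + 2 + 2 + 1 + 1 + 1 + 1 = 28. The instruction does not give 24; the gap is 28 - 24 = 4. A row lost in reading the PDF could not explain it, since a further row would raise the sum.

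**Step 2. Look for a rule that does give 24.**
- Only the cancer pair counted once: 28 - 2 = 26. No match.
- Only the liver pair counted once: 28 - 2 = 26. No match.
- Both pairs counted once, at the more severe line: 28 - 2 - 2 = 24. Match.

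The cancer double count thus explains 2 of the 4 excess points, and the liver lines explain the other 2.

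**Step 3. Effect on a trial patient with no other comorbidity.**
- Printed instruction: 6 + 2 = 8.
- Rule implied by the 24-point scale: 6.
- Difference: 2 points.

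**Step 4. When the difference matters.**
Let d be the extra points given at an assessment, either 0 or 2.
- If d = 2 for everyone at every visit, the between-arm difference shifts by 2 - 2 = 0 and the change from baseline shifts by 2 - 2 = 0. Only the reported level is wrong.
- If d = 0 at one visit and d = 2 at the next, the patient shows a false change of +2; in the reverse order, -2.
- If one site uses d = 0 and another d = 2, patients with identical health differ by 2.

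**The case against.** The strongest reply is that nothing decisive rests on this score. Comorbidity eligibility uses the CISR-G, and the other frailty criteria are ADL, 4-IADL, BMI or weight loss, and the timed up and go test. Stratification uses LATITUDE risk and ECOG status. The primary and key secondary endpoints do not contain the index, and section 10.3.7 treats all endpoints beyond the key secondary ones as exploratory. Section 10.3.5 attaches no hypothesis, cut-off or test to it. All of this stands and limits the point to a minor one.

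It is also fair to say that the cancer lines are constant across patients, so a uniform double count cancels (step 4). That stands too. It does not make the reported level right, and the form does not secure uniform use. Section 6.3 presents the G-CODE as a means of comparison across trials, and a constant extra 2 points would not serve that purpose.

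The liver pair will seldom matter, because non-inclusion criterion 13 excludes known chronic liver disease at screening.

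Three stronger readings are tempting, and the documents do not support them:

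- **That 24 is possible only if each pair counts once.** Dropping a single 4-point line, such as AIDS/HIV, also leaves 24, and other combinations worth 4 exist. The paired reading is the most plausible because these are the only two pairs on the form that grade one condition, but it is an inference. The form follows a cited publication that is not at hand.
- **That the baseline scores of all 300 patients are on mixed scales.** This would need evidence that raters tick differently. The documents give none, so it is a risk and not a finding.
- **That the score's reliability is reduced by a known amount.** Any such figure needs a double-tick rate and a standard deviation of the score, and the protocol gives neither.

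One could add that totals are usually derived under the SAP or the eCRF specification, which are not shown. That may limit the damage, but the instruction to sites stands in the protocol and contradicts the scale printed with it.

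**Conclusion.** The point holds as a minor error in a data-collection form. The instruction yields a maximum of 28 against a stated 24, and 8 points for the study cancer where the form's scale implies 6. Every patient scored as instructed is therefore 2 points too high on the form's own scale. The figure of 6 rests on the inference that the more severe line of each pair replaces the milder one; the mismatch between 28 and 24 needs no inference.

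A false 2-point difference or change can arise only where raters read the form differently between sites or visits, and how often that happens is unknown. A reader might infer a threat to the treatment comparison. There is none to see: the trial is randomised and double-blind, nothing suggests that ticking would differ by arm, and no eligibility, stratification, primary or key secondary result uses the score.

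**What to change.** In Appendix 8 section 7, add one sentence: of each graded pair only the more severe line is counted, so metastatic tumour is not added to any malignancy, and moderate/severe liver disease is not added to mild. Keep the total out of 24.

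Derive the total centrally from the ticked items for all patients, including those already enrolled (about 115 of 300 at the current amendment), so that it no longer depends on how a rater added up.

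The cost is one sentence and one derived variable. No new data are needed if the individual ticks are stored, which the protocol does not state. If only totals were kept, sites would have to be asked for the items, because a total of 8 may mean a double count or the cancer plus one genuine 2-point condition. The number of records to correct grows with each visit.

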### Clinical condition

	Metastatic solid tumour	6 points
	AIDS / HIV	4 points
	Moderate / severe liver disease	4 points
	Any malignancy, including leukemia and lymphoma	2 points
	Mild liver disease	2 points
	Hemiplegia or paraplegia	2 points
	Congestive heart failure	2 points
	Dementia	2 points
	Chronic pulmonary disease	1 point
	Rheumatologic disease	1 point
	Renal disease	1 point
	Diabetes with chronic complications	1 point

Score   / 24

## Appendix 9. Cumulative Illness Score Rating-Geriatrics (CISR-G)

Online calculator available: <https://www.mdcalc.com/cumulative-illness-rating-scale-geriatric-cirs-g>

### SCORING SHEET

Instructions: Please refer to the CIRS-G manual. Write brief descriptions of the medical problem(s) that justified the endorsed score on the line following each item.

#### Rating strategy

0 = No problem

1 = Current mild problem or past significant problem

2 = Moderate disability or morbidity/requires first line therapy

3 = Severe/ constant significant disability/ uncontrollable chronic problems

4 = Extremely severe/ immediate treatment required/ end organ failure/ severe impairment in function

#### Score calculation

Category	Description	Score
Heart	_____	_____
Vascular	_____	_____
Haematopoietic	_____	_____
Respiratory	_____	_____
Eyes, Ears, Nose Throat & Larynx	_____	_____
Upper GI	_____	_____
Lower GI	_____	_____
Liver	_____	_____
Renal	_____	_____
Genitourinary	_____	_____
Musculoskeletal/Integument	_____	_____
Neurological	_____	_____
Endocrine/metabolic & Breast	_____	_____
Psychiatric illness	_____	_____
Total number of categories endorsed		_____
Total score		_____
Severity index		_____
(total score/total number of categories endorsed)		_____
Number of categories at level 3 severity		_____
Number of categories at level 4 severity		_____

**A MANUAL OF GUIDELINES FOR SCORING THE CUMULATIVE ILLNESS RATING SCALE  
FOR GERIATRICS (CIRS-G)**

MAY 1991

Written by

[name]. with [name].

University of Pittsburgh

School of Medicine

Department of Geriatric Psychiatry

Western Psychiatric Institute and Clinic

[name]

[name]

## PHILOSOPHY AND DEVELOPMENT OF THE SCALE

Compiling and quantifying medical problems in the elderly population would allow meaningful comparison of medical burden and treatment outcomes in elderly patients with variable and complex medical problems. The Cumulative Illness Rating Scale (CIR), developed by Lin, Lin and Gurel, published in JAGS in 1968  appealed to the writers intuitively as a user friendly but comprehensive review of medical problems by organ system, based on a 0 thru 4 rating, yielding a cumulative score. This scale was revised to reflect common problems of the elderly with an emphasis on morbidity using specific examples and was renamed the Cumulative Illness Rating Scale for Geriatrics (CIRS-G).

Some "arbitrary" decisions were made for categorizing certain conditions that could overlap more than one category and thus be counted twice, e.g., dementia is categorized in psychiatry although it overlaps with neurology, vertigo in the Ear, Nose and Throat category although it could also be in neurology, and CNS vascular lesions are confined to neurology although they technically overlap with "vascular." See individual sections of the manual for further details.

## EDUCATION OF RATER

Nurses, physician assistants, nurse practitioners or physicians are required to have the necessary background for completing this scale. Due to the judgement required, some physician consultation may be necessary to clarify complex medical problems or their severity.

## THE MINIMUM DATABASE REQUIRED

It is expected that every patient have a complete history and physical with a designated problem list, height, weight, and baseline labs including a complete blood count and differential, chem profile to include electrolytes, liver and kidney function, serum B12, thyroid function, cholesterol level, and an EKG. For rating psychiatric conditions the rater is expected to be familiar with the Folstein Mini-Mental Status Exam (Folstein, Folstein, & McHugh, 1975 ) and the Diagnostic and Statistical Manual III-R (DSM III-R) .

Other information of more specialized nature will increase the accuracy of the rating in a given patient and should be used when available. Scoring "live" patients (rather than retrospective chart reviews) is recommended to be able to clarify points that could differentiate two score levels more accurately.

## RATING STRATEGY

Scoring contingencies for every possible medical problem is obviously too cumbersome and quickly exhausts efforts to maintain simplicity and ease of use. The CIRS-G scale seeks to outline intuitive severity levels within each category to serve as a guide for the rater to interpolate the particular problem set of a given patient. We acknowledge that judgement is ultimately required for a "best fit" and that rigorous specificity may be traded off for the intuitive "face validity" and ease of use of this scale.

## SCORING

Scoring was modified in the CIRS-G to yield five numbers: the total number of categories endorsed, the total score, the ratio of total score/number of endorsed categories (yielding a severity index per category), and the number of categories at level 3 and 4 for a given patient. This rating strategy allows the reader to see at a glance whether a given patient's total score reflects a few serious problems or multiple problems of mild to moderate severity as well as potential severe problems that merit a 3 or 4 rating. A single page scoring sheet also provides a rating for each organ system as well as space for a brief written description of the particular problem that merited the score (See sample scoring sheet).

Space provided on the scoring sheet is intended for a brief description of the problem that merited the endorsed score to facilitate more detailed retrospective analysis.

## RATING ACTIVE VS CHRONIC PROBLEMS

Repeating this scale on the same patient at two different points of time may show a decline in total score if there were acute problems at time 1 that had resolved at time 2, however, this scale is clearly weighted toward chronic problems (including "status post" diagnoses) and is therefore cumulative such that the CIRS-G score will generally increase over time in a given patient.

## RATING SUGGESTIONS (GENERAL)

We have found it easier to rate the severity of medical problems within a category by defining "mild" and "extremely severe" first, i.e., 1 and 4 and subsequently "moderate" and "severe," (2 and 3). The bulk of judgement, in our experience, rests in differentiating 2 and 3.

Note the following descriptors for a given level of severity:

0 - No Problem,

1 - Current mild problem or past significant problem

2 - Moderate disability or morbidity/ requires "first line" therapy

3 - Severe/constant significant disability/ "uncontrollable" chronic problems

4 - Extremely Severe/immediate treatment required/end organ failure/severe impairment in function

### Level 1 - Current mild problem or past significant problem.

Any current medical problem that causes mild discomfort or disability, or has occasional exacerbations that have an overall minor impact on morbidity should be rated a "1," for example, a hiatal hernia with occasional heartburn treated with prn antacids. Medical problems that are not currently active but were significant problems in the past should also be listed as a "1," for example, passage of a kidney stone. Past childhood illnesses, minor surgery, uncomplicated healed fractures, minor injuries, teeth extractions, or events so remote without sequelae (e.g., one febrile seizure in childhood) need not be listed at all. However, if any of the above leave a suspicion of potential future complications the rater should err on the side of inclusion, and briefly describe his/her concerns in the space provided.

### Level 2 - Moderate disability or morbidity/requires "first line" therapy.

Level 2 should be endorsed for medical conditions that require daily medication of "first line" nature, for example, patients requiring daily nonsteroidal anti-inflammatory drugs for arthritis or daily digoxin to control congestive heart failure.

### Level 3 - Severe/constant significant disability/"uncontrollable" chronic problems.

Level 3 should be endorsed for chronic conditions that are not compensated for with first line therapy, for example, requiring steroids for rheumatologic conditions or lung disease. "Constant significant disability" describes patients whose underlying pathology is not fully compensated by medical regimens, for example, patients with exertional angina would endorse a level "3" because their underlying pathology is not fully compensated by medical regimens but many less strenuous activities are possible (i.e., level "4" is not indicated).

### Level 4 - Extremely Severe.

Immediate treatment required/end organ failure/severe impairment in function. This level describes the late stages of disease or disability within a category. Generally, this level reflects the failure to arrest the disease process with resulting disability, pain, or restricted activities of daily living (ADL's). Alternatively, any acute condition that requires immediate treatment e.g., bladder outlet obstruction would also qualify as a "4." Severely limited ambulation or ADL's or sensory impairment would also endorse a "4," in the appropriate category for example, blindness, deafness or being wheelchair bound.

